4.1.5 ANALYSES TO ADDRESS PRIMARY AND SECONDARY OBJECTIVES

4.1.6 DESCRIPTIVE ANALYSES

For each study measure descriptive statistics within each randomised group and overall will be presented for data at each study time point.

Table 2. –Characteristics (M0 Day 0 measurements) of the participants by vaccine group

Characteristic	R21/Matrix-M™ + DHA-PIP + SLD-PQ n=X	R21/Matrix-M™ n=X	No Vaccine n=X
Gender n (% male)			
Age (years): median (range)			
Weight (kg): median (range)			
QTc int (msec): median (range)			
Fever n (%)			
Hb mean (sd)			
WBC median (range)			
Platelets median (range)			
Creatinine median (range)			
AST median (range)			
ALT median (range)			
Temperature mean (sd)			

4.1.7 ANALYSIS OF IMMUNOGENICITY

The serum anti-CS antibody titre and avidity responses for each treatment arm will be compared to the titre before vaccine administration as outlined in tables 2a, 2b, 3a and 3b below. In addition, immunology will be analyzed and compared in terms of the potential parameters using appropriate statistics according to the data structure in which data will be presented to the statistician. While the final choice of immunologic assays will be determined at a later stage the may include the following:

- *Plasmodium falciparum*. Circumsporozoite Protein. (NANP)6 Ab.IgG
- *Plasmodium falciparum*. Circumsporozoide Protein. (NANP)6 Ab.IgG Avidity
- *Plasmodium falciparum*. anti-C-Term Circumsporozoide Ab.IgG
- *Plasmodium falciparum*. anti-C-Term Circumsporozoide Ab.IgG avidity
- *Plasmodium falciparum*. Circumsporozoite Full length (N+C-Terminal)
- *Plasmodium falciparum*. anti-full length CSP Ab.IgG avidity

The serum anti-CS antibody titre -Proportion in study group with >4-fold rise in titre from baseline to: One month after first dose; One month after second dose; One month after the third dose; Six Months after the first dose for all groups.

Table 3ai. *Plasmodium falciparum*. Circumsporozoite Protein.(NANP)6 Ab.IgG

ARM	1 month after 1 st dose n (%)	1 month after 2 nd dose n (%)	1 month after 3 rd dose n (%)	6 months after 1 st dose n (%)
R21/Matrix-M™ + DHA-PIP + SLD-PQ				
R21/Matrix-M™				
No vaccine				

Table 3aii. *Plasmodium falciparum*. anti-C-Term Circumsporozoide Ab.IgG

ARM	1 month after 1 st dose n (%)	1 month after 2 nd dose n (%)	1 month after 3 rd dose n (%)	6 months after 1 st dose n (%)
R21/Matrix-M™ + DHA-PIP + SLD-PQ				
R21/Matrix-M™				
No vaccine				

Table 3aiii. *Plasmodium falciparum*. Circumsporozoite Full length (N+C-Terminal)

ARM	1 month after 1 st dose n (%)	1 month after 2 nd dose n (%)	1 month after 3 rd dose n (%)	6 months after 1 st dose n (%)
R21/Matrix-M™ + DHA-PIP + SLD-PQ				
R21/Matrix-M™				
No vaccine				

AVIDITY

Avidity -Proportion in study group with >4-fold rise from baseline to: One month after first dose; One month after second dose; One month after the third dose; Six months after the first dose for all the three groups. These will be summarised in tables 2bi to 2bii as follows:

Table 3bi. *Plasmodium falciparum*. Circumsporozoide Protein.(NANP)6 Ab.IgG Avidity

ARM	1 month after 1 st dose n (%)	1 month after 2 nd dose n (%)	1 month after 3 rd dose n (%)	6 months after 1 st dose n (%)
R21/Matrix-M™ + DHA-PIP + SLD-PQ				
R21/Matrix-M™				
No vaccine				

Table 3bii. *Plasmodium falciparum*. anti-C-Term Circumsporozoide Ab.IgG avidity

ARM	1 month after 1 st dose n (%)	1 month after 2 nd dose n (%)	1 month after 3 rd dose n (%)	6 months after 1 st dose n (%)
R21/Matrix-M™ + DHA-PIP + SLD-PQ				
R21/Matrix-M™				
No vaccine				

Table 3biii. *P falciparum*. anti-full length CSP Ab.IgG avidity

ARM	1 month after 1 st dose n (%)	1 month after 2 nd dose n (%)	1 month after 3 rd dose n (%)	6 months after 1 st dose n (%)
R21/Matrix-M™ + DHA-PIP + SLD-PQ				
R21/Matrix-M™				
No vaccine				

The frequency and the proportions of participants who are seropositive* for antibodies at each timepoint will be summarized in the table below

Table 3ci. Proportion seropositive* for antibodies at each timepoint: *Plasmodium falciparum*.
Circumsporozoite Protein.(NANP)6 Ab.IgG

ARM	1 month after 1 st dose n (%)	1 month after 2 nd dose n (%)	1 month after 3 rd dose n (%)	6 months after 1 st dose n (%)
R21/Matrix-M™ + DHA-PIP + SLD-PQ				
R21/Matrix-M™				
No vaccine				

* The percentage of subjects seroconverting after each immunization based on a value greater than the mean titer at baseline (before immunization # 1) plus 2 standard deviations for all subjects included in the analysis.

Table 3cii. Proportion seropositive* for antibodies at each timepoint: *Plasmodium falciparum*.
anti-C-Term Circumsporozoide Ab.IgG

ARM	1 month after 1 st dose n (%)	1 month after 2 nd dose n (%)	1 month after 3 rd dose n (%)	6 months after 1 st dose n (%)
R21/Matrix-M™ + DHA-PIP + SLD-PQ				
R21/Matrix-M™				
No vaccine				

* The percentage of subjects seroconverting after each immunization based on a value greater than the mean titer at baseline (before immunization # 1) plus 2 standard deviations for all subjects included in the analysis.

Table 3ciii. Proportion seropositive* for antibodies at each timepoint: *Plasmodium falciparum*.
Circumsporozoite Full length (N+C-Terminal)

ARM	1 month after 1 st dose n (%)	1 month after 2 nd dose n (%)	1 month after 3 rd dose n (%)	6 months after 1 st dose n (%)
R21/Matrix-M™ + DHA-PIP + SLD-PQ				
R21/Matrix-M™				
No vaccine				

* The percentage of subjects seroconverting after each immunization based on a value greater than the mean titer at baseline (before immunization # 1) plus 2 standard deviations for all subjects included in the analysis.

The serum anti-CS antibody titre

The serum anti-CS antibody titre -The geometric mean-in titre from baseline to: One month after first dose; One month after second dose; One month after the third dose; Six months after the first dose for all groups.

Table 4ai. *Plasmodium falciparum*. Circumsporozoite Protein.(NANP)6 Ab.IgG

ARM	1 month after 1 st dose Geometric Mean (95 % CI)	1 month after 2 nd dose Geometric Mean (95 % CI)	1 month after 3 rd dose Geometric Mean (95 % CI)	6 months after 1 st dose Geometric Mean (95 % CI)
R21/Matrix-M™ +DHA-PIP + SLD-PQ				
R21/Matrix-M™				
No vaccine				

Table 4aii. *Plasmodium falciparum*. anti-C-Term Circumsporozoide Ab.IgG

ARM	1 month after 1 st dose Geometric Mean (95 % CI)	1 month after 2 nd dose Geometric Mean (95 % CI)	1 month after 3 rd dose Geometric Mean (95 % CI)	6 months after 1 st dose Geometric Mean (95 % CI)
R21/Matrix-M™ + DHA-PIP + SLD-PQ				
R21/Matrix-M™				
No vaccine				

Table 4aiii. *Plasmodium falciparum*. Circumsporozoite Full length (N+C-Terminal)

ARM	1 month after 1 st dose Geometric Mean (95 % CI)	1 month after 2 nd dose Geometric Mean (95 % CI)	1 month after 3 rd dose Geometric Mean (95 % CI)	6 months after 1 st dose Geometric Mean (95 % CI)
R21/Matrix-M™ + DHA-PIP + SLD-PQ				
R21/Matrix-M™				
No vaccine				

AVIDITY (Geometric means)

Avidity -The geometric mean in titre from baseline to: One month after first dose; One month after second dose; One month after the third dose; Six months after the first dose for all groups.

Table 4bi. *Plasmodium falciparum*. Circumsporozoide Protein.(NANP)6 Ab.IgG Avidity

ARM	1 month after 1 st dose Geometric Mean (95 % CI)	1 month after 1 st dose Geometric Mean (95 % CI)	1 month after 3 rd dose Geometric Mean (95 % CI)	6 months after 1 st dose Geometric Mean (95 % CI)
R21/Matrix-M™ + DHA-PIP + SLD-PQ				
R21/Matrix-M™				
No vaccine				

Table 4bii. *Plasmodium falciparum*. anti-C-Term Circumsporozoide Ab.IgG avidity

ARM	1 month after 1 st dose Geometric Mean (95 % CI)	1 month after 2 nd dose Geometric Mean (95 % CI)	1 month after 3 rd dose Geometric Mean (95 % CI)	6 months after 1 st dose Geometric Mean (95 % CI)
R21/Matrix-M™ + DHA-PIP + SLD-PQ				
R21/Matrix-M™				
No vaccine				

Table 4biii. *P falciparum*. anti-full length CSP Ab.IgG avidity

ARM	1 month after 1 st dose Geometric Mean (95 % CI)	1 month after 2 nd dose Geometric Mean (95 % CI)	1 month after 3 rd dose Geometric Mean (95 % CI)	6 months after 1 st dose Geometric Mean (95 % CI)
R21/Matrix-M™ + DHA-PIP + SLD-PQ				
R21/Matrix-M™				
No vaccine				

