Currently there are no safety and immunogenicity data for the use of R21/Matrix-M™ in an Asian population. This trial will provide preliminary data to support a larger trial. For integration with the current Targeted malaria elimination (TME) activities, which provide mass drug administrations at months M0, M1, and M2, it would be most efficient and practical to provide the vaccine at the same intervals.

In summary: We propose to conduct a safety and immunogenicity trial of R21/Matrix-M™ in Thai adults. The major aims of this study are to: (1) assess the safety and immunogenicity of R21/Matrix-M™ in Thai adults, (2) confirm that the co-administration of antimalarial drugs with the malaria vaccine R21/Matrix-M™ does not reduce the immunogenicity of the vaccine, and (3) assess

**Research Proposal Submission Form
for a study involving human subject enrollment WITH
specimen collection**

Document No.: FTM ECF-033-01

Page 9 of 52

pharmacokinetics of antimalarial drug combination dihydroartemisinin/ piperaquine, and SLDPQ in subjects who concurrently receive R21/Matrix-M™.

B2. STUDY OBJECTIVES

B2.1 Primary Objective

- To assess the safety of the R21/Matrix-M™ vaccine, with and without concurrent anti-malarial administration, in Thai adults.

B2.2 Secondary Objectives

- To compare the immunologic response to R21/Matrix-M™ vaccine when concurrently given with DHA-PIP + SLD-PQ (Arm 1) with R21/Matrix-M™ vaccine alone (Arm 2) in Thai adults.
- To compare the piperaquine levels of participants who received the antimalarial drugs alone (Arm 3) with participants who received the antimalarial drugs combined vaccine (Arm 1).

B3. STUDY SITE(S)

Clinical study site:

This study will be conducted at the Clinical Therapeutics Unit (CTU), Hospital for Tropical Diseases, Faculty of Tropical Medicine, Mahidol University.

B4. STUDY TIMELINES:

We will recruit volunteers into this study after ethical approvals are granted from the Oxford Tropical Research Ethics Committee (OXTREC), and the Ethics Committee, Faculty of Tropical Medicine, Mahidol University. The volunteers will be included in this study for up to 7 months. We expect the recruitment period, data collection procedures, and to complete laboratory procedures and analysis approximately 18 months. The total duration for this study including preparations, regulatory approvals, and report writing is expected to be approximately 24 months.

B5. STUDY POPULATION AND SAMPLE

B5.1 Target population

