The sample size calculations are based on the objective of comparing the serologic response to R21/Matrix-M™ vaccine concurrently given with DHA-PIP + SLD-PQ with R21/Matrix-M™ vaccine alone in adults instead of basing it on safety outcome. This is a Phase II trial. Sample sizes for Phase II trials are usually small, as safety is still of paramount importance. Because of this limitation, these phase II studies are usually powered on the immunogenicity/efficacy endpoints because safety events are rare and a sample size based on safety would lead to a very high sample size that would not be acceptable from ethical standpoint. Another reason why powering it on immunogenicity/efficacy (a co-primary objective) is important, is that if the vaccine has poor immunogenicity profile then the safety question becomes redundant unless the study is a non-inferiority trial. We are optimistic that this sample size will be able to reveal important safety signals between arms which can be further explored in a phase III trial which would be a large trial that may be powered on safety endpoints that are rare. The efficacy endpoint (Immunogenicity objective) is a co-primary objective to the safety objective. We include both “safety” and “immunogenicity” terms in the study title because both of them are key endpoints. Valid sample sizes for comparing sample sizes between two groups are usually obtained using exact test methods such as the Fisher's exact test power calculations. This is done using simulations as sample size formulas are not well developed. To estimate the sample size we use a four-fold increase in anti –CS antibody titre as an assumed correlate of protection. For the sample size calculation, we assume that the background rate of response in the reference groups will be 5% and the true rate of anti-CS antibody response in the vaccine groups is 80%. We wish to exclude, for the vaccine, a one-tailed lower 95% CI for the reference-vaccine group difference of lower than 30%. The study aims to detect this difference with

**Research Proposal Submission Form
for a study involving human subject enrollment WITH
specimen collection**

Document No.: FTM ECF-033-01

Page 12 of 52

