**Research Proposal Submission Form
for a study involving human subject enrollment WITH
specimen collection**

Document No.: FTM ECF-033-01

Page 30 of 52

- Participants vaccinated with the wrong study agent (non-compliance with the randomization code)
- Participants excluded from the intention-to-treat analysis.
- No interim analysis is planned.

B6.7.5 Analysis of baseline characteristics

The demographic characteristics of enrolled participants will be compared by study group.

B6.7.6 Analysis of immunogenicity

The serum anti-CS antibody titre and avidity

The main analyses will involve the serum anti-CS antibody titre and avidity. These parameters will be measured at baseline and then at follow-up times longitudinally. During statistical analysis, we will assess whether a participant had a titre that is greater than 4 times that of the participant's baseline titre. Then we will compute the number of participants who had a titre of greater than 4 times their baseline titres and obtain a proportion of these for each group. These proportions of participants with >4-fold rise in titre from baseline will be compared between arms at each follow-up time. A Fisher's exact test will be used to compare the proportions of participants with >4-fold rise in titre from baseline between groups at each follow-up. These proportions will also be summarised graphically by arm to visually assess the differences between arms over-time. This will help to visually assess whether time modifies the effect of group.

Furthermore, the absolute titre values will be analysed and compared between groups. Since the distribution of these titre values will likely be highly skewed overtime, these values will be log-transformed and compared between arms at the different follow-up times. In order to revert back to the original scale (taking exponentials), the Geometric Mean Ratios (GMR) of the titres will be the measures of effect of interest that will be used to compared the log-transformed titres between the arms. The 95% confidence intervals for the Geometric Mean Ratios will be presented. The mean titre trends (on log-scale) over time will also be plotted by arm to assess whether there is a difference in trends of the titres between arms over time.

Tests of significance will be performed at 5% significance level. Analyses will be performed in Stata version 17 or higher. A separate detailed Statistical Analysis plan will be developed, finalized and signed before databased lock.

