1 INTRODUCTION

This study is a randomized, open-label, single centre, Phase 2 trial of R21/Matrix-M™. A total of 120 healthy non-pregnant Thai adults, aged 18-55 years, inclusive, will be enrolled and randomised to one of three study groups:

- Arm 1: R21/Matrix-M™ in subjects who concurrently receive co-formulated dihydroartemisinin/piperaquine + single low dose of primaquine (SLDPQ).
- Arm 2: R21/Matrix-M™ alone.
- Arm 3: Co-formulated dihydroartemisinin/piperaquine + SLDpq

We propose to conduct a safety and immunogenicity trial of R21/Matrix-M™. The major aims of this study are to: (1) assess the safety and immunogenicity of R21/Matrix-M™ in healthy Thai adults, (2) confirm that the co-administration of antimalarial drugs with R21/Matrix-M™ does not reduce the immunogenicity of the vaccine, and (3) assess the pharmacokinetics of antimalarial drug: piperaquine in subjects who concurrently receive R21/Matrix-M™. This study will contribute to our understanding of the immunogenicity of a vaccine, which could potentially be used to help stop the spread of malaria and anti-malarial resistance in the region.

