2.1.2 SECONDARY OBJECTIVES

- To compare the immunologic response to R21/Matrix-M™ vaccine when concurrently given with DHA-PIP + SLD-PQ (Arm 1) with R21/Matrix-M™ vaccine alone (Arm 2) in Thai adults.
- To compare the piperaquine levels of participants who received the antimalarial drugs alone (Arm 3) with participants who received the antimalarial drugs combined vaccine (Arm 1).

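### Both documents aim to confirm that antimalarials do not reduce vaccine immunogenicity, but neither sets a limit that Arm 1 v Arm 2 must exclude, and SAP 4.1.7 does not carry forward the protocol's between-arm comparisons

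*SAP*

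**What the plan says.** **Aim.** Protocol B1 sets out to "confirm that the co-administration of antimalarial drugs with the malaria vaccine" does no harm to the antibody response. Protocol A10.1 has the same aim, and SAP 1 says co-administration "does not reduce the immunogenicity of the vaccine".

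**Objective.** Protocol B2.2 and SAP 2.1.2 word it more neutrally: "To compare the immunologic response to R21/Matrix-M™ vaccine when concurrently given with DHA-PIP + SLD-PQ (Arm 1"), against the vaccine given alone in Arm 2.

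**Sizing.** Protocol B5.3 and SAP 2.1.5 size Arms 1 and 2 to detect 50% v 80% with a more than four-fold rise: 50 per arm, Fisher's exact test, 5% level, stated power 85%. The one bound to be excluded in either document, 30 points, is for the vaccine groups against the no-vaccine reference, and it leads to the 20 participants in Arm 3.

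**Analysis in the protocol.** B6.7.6 gives two between-arm comparisons at each follow-up. The first is Fisher's test on the responder proportions. The second is on log titres, where "the Geometric Mean Ratios (GMR) of the titres will be the measures of effect of interest", presented with 95% confidence intervals. Tests are at the 5% level.

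**Analysis in the SAP.** Section 4.1.7 opens: "The serum anti-CS antibody titre and avidity responses for each treatment arm will be compared to the titre before vaccine administration". Its table shells show n (%) and geometric mean (95% CI) by arm at four visits, with no column for a ratio, difference or p-value. Its other wording on method is that "immunology will be analyzed and compared in terms of the potential parameters using appropriate statistics according to the data structure". The GMR appears nowhere in the SAP, and Fisher's test appears there only in the sample size section.

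**Status.** Protocol B5.3 says "The efficacy endpoint (Immunogenicity objective) is a co-primary objective to the safety objective", and SAP 2.1.5 agrees. SAP 3.2 lists antibody concentration as a primary outcome at Months 1 and 2. Protocol B2.2 and SAP 2.1.2 make the comparison a secondary objective, and protocol B6.3.2 makes it a secondary endpoint at Months 1, 2, 3 and 6.

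**The concern.** To confirm that something is not reduced is to claim that any loss is smaller than some limit. That needs a stated limit and a confidence bound that clears it. A test of difference cannot supply this, because it can fail to reach significance when the loss is real.

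The comparison written in SAP 4.1.7 is a step further away. Titres in both vaccine arms can rise well above baseline while Arm 1 rises less than Arm 2, and a contrast of each arm with its own pre-vaccine titre would not show it. The SAP is the document in which the between-arm method should be fixed, and leaving it to suitable statistics once the data structure is known means choosing it late.

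Arms 1 and 2 hold 100 of the 120 participants and were sized on this comparison. The data will be usable in any case. What lacks a pre-specified basis is the conclusion that the aim announces.

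**Working it through.** **1. The plan's own figure.** Inputs from protocol B5.3 and SAP 2.1.5: 50 per arm, 50% v 80%, Fisher's exact test, 5% level. Sidedness is not stated. Exact power is the sum over all (x1, x2) of Bin(x1; 50, p1) × Bin(x2; 50, p2), counting tables with Fisher p ≤ 0.05. With p1 = 0.50 and p2 = 0.80 the two-sided result is 85.3%, matching the stated 85%. The one-sided version gives 91.7%, so the two-sided test is the one that reproduces.

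**2. The same test at smaller true losses.** Arm 2 is held at 80%, the documents' own assumption.

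| Arm 1 true rate | Loss (points) | Power | Non-significant |
|---|---|---|---|
| 50% | 30 | 85.3% | 14.7% |
| 60% | 20 | 51.5% | 48.5% |
| 65% | 15 | 31.6% | 68.4% |
| 70% | 10 | 15.5% | 84.5% |

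**3. What a non-significant result can hide.** Take 32/50 in Arm 1 and 40/50 in Arm 2. Fisher p = 0.12. The Wilson intervals are 0.501 to 0.759 and 0.670 to 0.888. Newcombe's limits for the difference of −0.16 are

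- lower: −0.16 − √[(0.640 − 0.501)² + (0.888 − 0.800)²] = −0.32
- upper: −0.16 + √[(0.759 − 0.640)² + (0.800 − 0.670)²] = +0.02

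The test is non-significant, yet a 32-point loss is not excluded.

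**4. How often that happens.** The benchmark is 30 points, the difference used for sizing. It is not a margin from the documents. The table gives the probability that the result is non-significant and also fails to exclude a 30-point loss, with the share of non-significant results in brackets.

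| Arm 1 true rate | Two-sided 95% limit | One-sided 95% limit |
|---|---|---|
| 60% | 26% (54%) | 16% (33%) |
| 65% | 25% (37%) | 13% (18%) |

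**5. What the trial could exclude.** With both arms truly at 80%, the lower two-sided 95% limit excludes a loss of 10, 15, 20 or 30 points with probability 23%, 47%, 71% and 97%. With a one-sided 95% limit these are 35%, 60%, 81% and 98%.

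**6. The GMR.** The documents give no SD, so a log10 SD of 0.3 to 0.6 is assumed. SE = SD × √(2/50) = 0.06 to 0.12. With t(98 df) = 1.984, the 95% CI is the estimate divided and multiplied by 10^(1.984 × SE) = 1.32 to 1.73. If the true GMR is 1, the chance that the lower limit clears a margin m comes from a noncentral t with noncentrality −log10(m)/SE:

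- m = 0.50: 0.301/0.06 = 5.02 to 0.301/0.12 = 2.51, giving over 99% down to 70%
- m = 0.67: 0.174/0.06 = 2.90 to 0.174/0.12 = 1.45, giving 82% down to 30%

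Both margins are illustrations only.

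**The case against.** Four points can fairly be made against this.

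- **The protocol still governs.** The SAP does not revoke B6.7.6, keeps the Arm 1 v Arm 2 objective, and tabulates responder proportions and geometric means by arm. This stands: the between-arm comparison is left unspecified in the SAP, not ruled out. A reader might infer that the SAP abandons it, which goes too far. But B6.7.6 attaches no limit to its interval either, so the missing rule remains under the protocol too.

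- **Nobody says a non-significant test will be read as confirmation.** Correct. A reader might infer that a difference test is the only decision the plan allows. The documents do not support that: B6.7.6 commits to presenting 95% CIs for the GMRs, and these show what loss is excluded. The 68% figure therefore describes what would follow if non-significance were read that way.

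- **The trial is preliminary.** Protocol B1 says "This trial will provide preliminary data to support a larger trial", the formal objective is only to compare, and neither document calls this a non-inferiority trial. This is a good argument for rewording the aim. It does not justify leaving the aim as it is.

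- **The size depends on choices.** The 30-point benchmark is borrowed, and a one-sided 95% limit, which is what the documents use for the vaccine v no-vaccine bound, lowers the joint probabilities to 13% and 16%. Both versions are shown for that reason. The 68% depends on neither choice.

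**Conclusion.** The point holds. The stated aim has no rule by which it could be met, and the one comparison SAP 4.1.7 spells out, each arm against its own baseline, cannot answer the Arm 1 v Arm 2 objective. It should be fixed, but it does not threaten the data.

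On size: if non-significance were taken as no reduction, a true 15-point loss would pass 68% of the time and a 20-point loss 48% of the time, assuming 80% response in Arm 2, 50 evaluable per arm and a two-sided Fisher test. The GMR figures rest further on an assumed SD.

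Three further readings are tempting and not supported. The sample size calculation is not wrong; its 85% reproduces. The 30-point bound in protocol B5.3 and SAP 2.1.5 is not a margin for Arm 1 v Arm 2; it concerns vaccine against no vaccine. And the protocol does not make the GMR the main analysis: B6.7.6 gives the responder comparison first, the arms were sized on responders, and the two are not ranked.

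The conflict over whether immunogenicity is co-primary or secondary is a separate inconsistency. It matters here only because it leaves unclear whether a confirmatory claim is intended.

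**What to change.** 1. **Restate both comparisons in SAP 4.1.7.** For Arm 1 v Arm 2, at the visits in protocol B6.3.2 and in the per-protocol (main) and intention-to-treat populations of SAP 4.1.4, give (a) the anti-NANP IgG GMR with 95% CI from log titres, and (b) the responder proportions with Fisher's test, adding a risk difference with 95% CI. The sponsor states which is main.

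2. **Match the aim to a rule.** Choose one:
   - Reword the aim in protocol A10.1 and B1 and SAP 1 as estimating the effect of co-administration, in line with the objective, and state that a non-significant test is not read as no reduction.
   - Keep the confirmatory aim, name one visit, and conclude that immunogenicity is not reduced only if the lower confidence limit of the main measure exceeds a margin that the sponsor justifies and fixes before database lock.

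3. **Consequential edit.** Give immunogenicity one status in both documents and reconcile the visits in SAP 3.2 with protocol B6.3.2.

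**Cost.** No new data. SAP 1, 3.2 and 4.1.7 change, and the protocol needs a wording amendment, which Appendix B 2.5 requires to be submitted and, where necessary, approved. Rewording gives up the confirmatory claim but needs no margin or single visit. The margin route may end inconclusive: for an illustrative GMR margin of 0.67, power is 82% to 30% over the assumed SD range.

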Vaccine and study medication accountability, storage, and handling will be in accordance with local SOPs. This study will not be blinded; i.e. it is an open-label study.

B6.2.2 Accountability of the study agents

The study site will maintain a record of the numbers of all vaccines and DHA/PIP + primaquine tablets obtained, used by the participants and returned to the pharmacy room in CTU. On study completion, a copy of the drug accountability record will be filed in the study folder.

B6.2.3 Concomitant medications

There will be no restrictions on concomitant medication beyond the exclusion criteria listed above.

B6.3 Study Endpoints

B6.3.1 Primary Endpoints

The safety of the investigational vaccine in each group:

- Occurrence of solicited from the date of each vaccination to 7 days of each vaccination.
- Occurrence of unsolicited adverse events (AEs) from the date of the first vaccination to 28 days after the last vaccination, according to the MedDRA classification.
- Occurrence of serious adverse events (SAEs) during the whole study period, i.e. during a 6-month follow up period from the receipt of first vaccination, according to the MedDRA classification.

B6.3.2 Secondary Endpoints

- For Arms 1 and 2, the concentration of antibodies against *Plasmodium falciparum* circumsporozoite (anti-NANP total IgG antibody), one month after the first dose (at Study month 1), one month after the second dose (at Study month 2), one month after the third dose (at Study Month 3) and six months after the first dose (at Study Month 6).
- Exploratory immunology endpoints including but not limited to cellular immunity.
- For Arms 1 and 3, piperaquine levels following the administration of the antimalarials with or without vaccine. (timepoints)

B6.4 Details of procedures for specimen/data collection

Procedures will be performed at the time points indicated in the schedule of procedures (Table 5). Additional procedures or laboratory tests may be performed, at the discretion of the investigators if clinically necessary (e.g. follow up repeat haematology or biochemistry laboratory tests in the event of clinically significant abnormal results).

Research Proposal Submission Form for a study involving human subject enrollment WITH specimen collection

Document No.: FTM ECF-033-01

Page 20 of 52

Table 5. Study Procedures

Timepoints	Month Day of month	Scr.	Study period																	
			M0				M1				M2				M3	M6 ^a				
			0 ^c	1	2	7	0	1	2	7	0	1	2	7	0	0				

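### The Arm 1 v Arm 2 antibody comparison is sized as one test at 5% but planned at four visits on two scales, with no single confirmatory comparison named.

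*SAP*

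**What the plan says.** **Sizing.** Protocol B5.3 and SAP 2.1.5 size Arms 1 and 2 on one comparison: Fisher's exact test, 50% v 80% with a four-fold rise, 50 per arm, 5% level, 85% power. No visit is given. The same text calls immunogenicity co-primary, although the objectives in both documents list it as secondary.

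**Testing.** Protocol B6.7.6 opens with "The main analyses will involve the serum anti-CS antibody titre and avidity". It uses Fisher's exact test to "compare the proportions of participants with >4-fold rise in titre from baseline between groups at each follow-up". It then compares log titres at the follow-up times, where "the Geometric Mean Ratios (GMR) of the titres will be the measures of effect of interest". It closes with "Tests of significance will be performed at 5% significance level". There is no testing order, no lead visit, no lead scale and no adjustment.

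**Visits.** Protocol B6.3.2 lists the antibody endpoint as secondary, for Arms 1 and 2, at Months 1, 2, 3 and 6. SAP 3.2 lists anti-CS antibody as a primary outcome, for all three groups, at Months 1 and 2 only. SAP 4.1.7 tabulates "One month after first dose; One month after second dose; One month after the third dose; Six Months after the first dose".

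**Assay.** Protocol B6.3.2 specifies anti-NANP total IgG and puts other immunology under exploratory endpoints. SAP 4.1.7 says "While the final choice of immunologic assays will be determined at a later stage" and then gives six that may be included, NANP IgG among them.

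**The concern.** The Arm 1 v Arm 2 comparison sets the sample size and answers the aim of showing that antimalarials do not reduce the antibody response. One test at 5% carries a false-positive chance of at most 5%. A set of tests over visits and scales carries more, unless one is designated in advance or the level is shared among them. Neither document does either.

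With no true difference, a significant result at one visit on one scale would be read as interference between the drugs and the vaccine. That could count against the combined vaccination and mass drug administration strategy that the trial is meant to inform. The two documents also disagree on which visits are primary, so a reader of the final report could not tell which result was meant to decide the question.

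**Working it through.** **Inputs from the documents:** 50 per arm; 50% v 80% for power; 80% assumed response in vaccinees; 5% level; four follow-ups; two scales. Sidedness is not stated; a two-sided test reproduces the stated power. **Assumed, because the documents give no value:** equal correlation between visits of 0.5 to 0.85.

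**1. The plan's own figure.** Exact enumeration of the two-sided Fisher test at 50% v 80%, 50 per arm, gives 85.3% power against 85% stated. It reproduces, for one test at one visit.

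**2. Simple bounds.** For k independent tests of actual size a, the chance of at least one false positive is 1 − (1 − a)^k.

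- Log titre, four visits: 1 − 0.95^4 = 18.5%.
- The two visits in SAP 3.2: 1 − 0.95^2 = 9.8%.
- Fisher's test is conservative, so its exact size was used: 2.8% at an 80% response, 1.8% at 90%, 0.7% at 95%. Over four visits, 80% gives 1 − (1 − 0.0282)^4 = 10.8%; 90% gives 1 − (1 − 0.0179)^4 = 7.0%; 95% gives 1 − (1 − 0.0072)^4 = 2.9%.

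**3. Allowing for correlation.** Null data were simulated for one assay, 50 v 50, at four visits, with a t-test on log titre and Fisher's test on responder status at an 80% response. Ranges cover repeat runs, which differ by about a percentage point.

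| Between-visit correlation | Log titre | Fisher, 80% response | Either scale |
|---|---|---|---|
| 0.5 | 15–16% | 10–11% | 20–21% |
| 0.7 | 13% | 10–11% | 18–19% |
| 0.85 | 10–11% | 9% | 15–16% |

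At a 95% response the Fisher column falls below 3%, while the log-titre column does not depend on the response rate. At a correlation of 0.9 the log-titre figure is still 9–10%.

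**4. What each remedy does to power** (Fisher, 50% v 80%, 50 per arm):

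- One named comparison at 0.05: 85.3%.
- Bonferroni over two visits, 0.05/2 = 0.025: 78.2%.
- Bonferroni over four visits, 0.05/4 = 0.0125: 69.8%.

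A fixed order of tests would also hold 5%, with no loss on the first test.

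**The case against.** Several points on the other side are sound, and they limit the claim.

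- A reader might infer that all six SAP assays at all four visits are tested at 5%, and quote a much larger error rate. The documents do not support this. The 5% sentence is in the protocol only. The SAP tables hold n (%) or geometric means with 95% CIs and have no p-value column, and SAP 4.1.7 introduces them as comparisons with the titre before vaccination. The SAP's word for further immunology is that it will be compared, "using appropriate statistics according to the data structure in which data will be presented to the statistician", which states neither a test nor a level.
- A reader might infer that the trial promises an overall 5% error rate and breaks it. It does not promise one: 5% is a per-test level, and the stated primary objective is safety, analysed by tabulation with exact intervals.
- A reader might infer that the assay and the method are wholly open. The protocol names anti-NANP total IgG, Fisher's test and the geometric mean ratio. The gap is that the SAP does not carry the named assay forward as fixed.
- A reader might infer that a chance finding is likely, or that results will be seen by arm before choices are made. For the named assay the chance is 10–16% on log titre, well short of likely. Allocation is open to participants and clinical investigators, but the assays are run in a UK laboratory, no interim analysis is planned, and nothing says by-arm antibody results will be released early. Equally, nothing rules it out: the SAP need only be signed before database lock.
- Fisher's test is conservative. If about 95% of vaccinees respond, its family over four visits stays under 5%. That protects the responder scale only; the log-titre comparisons still exceed 5%.

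What stands is narrower: one sized test, several planned tests on the named assay, and no statement of which one decides.

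**Conclusion.** The point holds for the named assay. The Arm 1 v Arm 2 comparison is powered as one test and planned as several, and the two documents disagree on its status and its visits. With no true difference, the chance of at least one nominally significant result over four visits is about two to three times 5% on log titre, about twice 5% by Fisher at the planned response rate, and three to four times 5% if either scale counts. These sizes rest on assumed correlations of 0.85 to 0.5, two-sided tests and full follow-up of 50 per arm. Avidity, which the protocol also calls a main analysis, would add to them and is not counted.

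The excess mainly raises the risk of a false alarm of interference; it does not by itself produce false reassurance. This is a clarification worth making before any antibody result is available, and it does not affect the safety objective.

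**What to change.** In SAP 3.2 and 4.1.7, and in protocol B6.7.6, name one confirmatory Arm 1 v Arm 2 comparison at 5%:

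- **Assay:** anti-NANP total IgG, as in protocol B6.3.2.
- **Visit:** one. Month 3, one month after the full series, is an example; SAP 3.2 should then be aligned with it.
- **Scale:** one. The >4-fold Fisher comparison matches the sizing and keeps 85% power. If the geometric mean ratio is preferred, restate the power for it.

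Report all other visits, assays and scales as estimates with 95% CIs and no significance claim. Limit the SAP sentence that defers the choice of assays to exploratory assays. Sign the SAP before any by-arm antibody result is released, and not merely before database lock.

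The cost is wording in the SAP and a protocol amendment to B6.7.6, with no extra participants or samples. The downside is that no significance claims can be made for the other visits, assays and scales.
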